8.2 Secondary Endpoints

Subjects who receive at least 2 cycles of belimumab are evaluable for secondary and explorative endpoints.

1. Incidence and severity of chronic GvHD at 6, 12 and 24 months after alloHCT

The presence of chronic GvHD will be determined according to the 2014 NIH Criteria (**Appendix B**). If chronic GvHD is diagnosed, each organ will be scored 0-3 and graded, according to the 2014 NIH criteria for Diagnosing and Staging of Chronic GvHD (**Appendix D**). These data will allow calculation of the NIH global severity score of mild, moderate or severe (**Appendix E**). Data will be collected on forms capturing chronic GvHD diagnosis and activity according to the 2014 NIH Criteria for chronic GvHD.

2. Incidence and severity of acute GvHD at 3 and 6 months after alloHCT

Acute GvHD will be graded according to modified Minnesota CIBMTR (**Appendix F**).

3. Overall survival at 6, 12 and 24 months after alloHCT

Overall survival will be determined from date of belimumab initiation, with death from any cause as the event of interest, and censoring at last follow up date for those with incomplete observations.

4. Relapse rate at 6, 12 and 24 months after alloHCT

Relapse rate will be determined from date of belimumab initiation and censoring at last follow up date for those with incomplete observations.

5. Overall corticosteroid requirement (dose and duration) for treatment of chronic GvHD at 6, 12 and 24 months after alloHCT

The dose of corticosteroids will be captured at each study visit.

6. Use of alternative treatment modalities for chronic GvHD at 6, 12 and 24 months after alloHCT

The use of additional systemic immune suppressive agents will be captured at each study visit.

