5 TREATMENT OF SUBJECTS AND STUDY DESIGN

This is a single center, open-label pilot and feasibility study of prophylactic belimumab for the prevention of chronic GvHD following alloHCT at Washington University School of Medicine in St. Louis. The study will include Screening Phase, Treatment Phase, and Follow-up Phase.

Subjects will be screened for the study after obtaining the results from their standard-of-care Day +30 bone marrow biopsy. Those subjects meeting the Inclusion and Exclusion Criteria will be enrolled in the study and start treatment between Day +30 and Day +80 after alloHCT. At enrollment, subjects may continue on steroids that were used to treat acute GvHD. At the time of enrollment, however, subjects should be responding to therapy and the dose of steroid should be ≤ 0.5 mg/kg/day of prednisone equivalent with no dose increase in the preceding 1 week. Subjects may also remain on other systemic immunosuppressive drugs that were used to prevent or treat acute GvHD. At the time of enrollment, acute GvHD should be grade II or less. Subjects diagnosed with or treated for chronic GvHD will be excluded from the study. The study population will include 10 subjects. Planned duration of treatment is for 7 cycles (6 months; see study schema). Subjects will be followed for 24 months. One of the secondary endpoints is to evaluate the impact of

belimumab on incidence and severity of chronic GvHD. The subjects who develop chronic GvHD while receiving treatment with the study drug, belimumab, may continue on the study at the discretion of treating transplant physician with careful documentation of their GvHD severity and treatments used for it. If at any point it is considered that the study drug may be contributing to chronic GvHD it will be discontinued.

The primary endpoint is safety and tolerability of belimumab. Subjects who receive at least one dose of belimumab will be eligible for primary endpoint analysis and it will be performed according to the CTCAE v4.03.

Diagnosis of chronic GvHD will be per NIH criteria (**Appendix B**). Those patients diagnosed with chronic GvHD will have organ specific staging and global scoring according to the NIH criteria (**Appendices D and E**).

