5.2 Study Drug Administration

Belimumab will be administered intravenously at 10 mg/kg over 1 hour. Enrollment and the first dose of belimumab (Cycle 1) will be administered between Day +30 and Day +80 after alloHCT, after reviewing bone marrow biopsy results and confirming eligibility. Subjects will receive belimumab every 2 weeks for 3 cycles and then every 4 weeks for a total of 7 cycles (6 months of therapy).

Therefore: Cycle 1 of belimumab will be administered between Day +30 and +60 after alloHCT, Cycle 2 will be administered 2 weeks later (+/- 3 days), Cycle 3 will be administered two weeks after Cycle 2 (+/- 3 days), and each subsequent cycle will be given every 4 weeks thereafter (+/- 1 week) for total of 7 cycles (6 months of therapy). This dosing and schedule of belimumab administration is similar to prior phase III studies for systemic lupus erythematosus [38, 39]. Subjects will continue to adjust their standard of care immunosuppressive medications at the discretion of treating physician.

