5.4 Duration of Therapy

Treatment may continue for six months, or until one of the following criteria applies:

- Documented and confirmed original hematologic disease relapse
- Death
- Adverse event(s) that, in the judgment of the investigator, may cause severe or permanent harm or which rule out continuation of study drug
- General or specific changes in the patient's condition render the patient unable to receive further treatment in the judgment of the investigator
- Grade III-IV acute GvHD not responding to therapy after 2 weeks
- Serious noncompliance with the study protocol
- Lost to follow-up
- Patient withdraws consent
- Investigator removes the patient from study
- The Siteman Cancer Center decides to close the study

If at any time the constraints of this protocol are considered to be detrimental to the patient's health and/or the patient no longer wishes to continue protocol therapy, the protocol therapy should be discontinued and the reason(s) for discontinuation documented in the case report forms. Subjects who prematurely discontinue treatment for any reason will be followed as indicated in the study calendar.

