Serious infections, including herpes zoster and opportunistic infections are rare, but possible. Infection prophylaxis should follow institutional guidelines. If patient develops infection requiring intravenous or intramuscular antibiotics, belimumab may be held for up to two weeks and will then be administered. If a patient needs a dose held for more than two weeks, the PI will be contacted to determine suitability for further study participation.

Rash with or without pruritus

Rash should be managed symptomatically according to standard medical practice. Patient should be evaluated for presence of acute GvHD (see guidelines below).

Elevation of liver enzymes

Elevation of liver enzymes is not listed as an expected adverse event with belimumab. However, elevated liver enzymes can occur in the context of acute GvHD and such patients should be evaluated for presence of acute GvHD.

Nausea and/or vomiting

Standard anti-emetics may be used for prophylaxis and treatment of nausea or vomiting.

Diarrhea

Diarrhea should be managed according to clinical practice. Patient should be evaluated for presence of acute GvHD (see guidelines below).

Depression and suicidality

Some autoimmune diseases have an increased risk of depression and suicidal behavior and/or ideation [Bachen, 2009; Timonen, 2003; Stenager, 1992]. For this reason, in studies of subjects with autoimmune disease, subjects should be assessed for depression, suicidal ideation and/or behavior at each visit by the treating physician (to be recorded in a physician note).

Progressive Multifocal Leukoencephalopathy (PML)

PML resulting in neurological deficits, including fatal cases, has been reported in SLE subjects receiving immunosuppressant pharmacotherapy, including belimumab. A

diagnosis of PML should be considered in any subject presenting with new-onset or deteriorating neurological signs and symptoms. The subject should be referred to a neurologist or other appropriate specialist for evaluation. If PML is confirmed, belimumab should be discontinued and consideration should be given to stopping immunosuppressant therapy.

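### Section 8.2 analyses only subjects who reach Cycle 2 but times OS and relapse from Cycle 1, so a death or confirmed relapse in the first two weeks or so drops out of the endpoint it belongs to

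*Combined protocol and SAP*

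**What the plan says.** The protocol uses two analysis sets. For the primary safety endpoint, Section 5 says "Subjects who receive at least one dose of belimumab will be eligible for primary endpoint analysis", and Section 8.1 agrees. For everything else, Section 8.2 opens with "Subjects who receive at least 2 cycles of belimumab are evaluable for secondary and explorative endpoints". Section 8.3 repeats the two-cycle condition for the correlative work.

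Within Section 8.2 the time origin for two endpoints is the first dose: "Overall survival will be determined from date of belimumab initiation, with death from any cause as the event of interest", and "Relapse rate will be determined from date of belimumab initiation and censoring at last follow up date".

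Section 5.2 schedules Cycle 2 two weeks after Cycle 1, with a window of three days either way. Section 5.7 allows a delay for an infection that needs parenteral antibiotics: "belimumab may be held for up to two weeks and will then be administered". Section 5.8 allows a hold of the same length for grade III-IV acute GvHD.

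The reasons for ending treatment in Section 5.4 include death, "Documented and confirmed original hematologic disease relapse", and "Adverse event(s) that, in the judgment of the investigator, may cause severe or permanent harm or which rule out continuation of study drug". They also include grade III-IV acute GvHD that has not responded after two weeks.

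Section 13 plans 10 subjects, no hypothesis test, and a 90% exact binomial interval for preliminary efficacy. It names roughly 100 banked institutional subjects as the comparator and says the data will be used for phase II sample size estimates. It gives no all-treated set, landmark or sensitivity analysis for the secondary endpoints.

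**The concern.** Membership of the analysis set is decided after the clock has started, by something that depends on the outcome. A subject must be alive, and without a confirmed relapse that ends treatment, to receive Cycle 2. For OS and relapse, then, the interval from Cycle 1 to Cycle 2 is immortal time, and an event inside it removes the subject instead of being counted.

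Stopping for toxicity or for unresolved acute GvHD before Cycle 2 has the same effect on membership. These subjects are likely to differ in prognosis from those who continue, so the exclusion is informative even when the endpoint itself has not yet occurred. One consequence is specific to acute GvHD: a subject whose grade III-IV disease never settles enough for Cycle 2 is dropped from the acute GvHD endpoint.

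Three things are at stake. Safety and efficacy may describe different subjects in the same small trial. The comparison with institutional controls puts a survive-and-continue condition on the treated side only. And the planning values for the next trial would come from the selected set.

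**Working it through.** **1. The plan's own figures.** With N = 10, the chance of at least one SAE at a true rate of 20% is 1 − 0.8^10 = 0.893, which matches the stated 90%. The chance of two or more at 5% is 1 − 0.95^10 − 10 × 0.05 × 0.95^9 = 0.086, below the stated 10%. Both reproduce. They concern the safety set and are unaffected by this point.

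**2. Length of the window.** From Section 5.2: 14 days, range 14 − 3 = 11 to 14 + 3 = 17. With a two-week hold (Sections 5.7 and 5.8): about 14 + 14 = 28 days.

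**3. Average bias from the window alone.** The documents give no survival rate, so 12-month OS from Cycle 1 is assumed at 60%, 70% or 80%, with constant hazard h = −ln(S12)/365.25. Requiring survival to day d changes 12-month OS from S12 to S12 / exp(−h·d).

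| Assumed 12-month OS | Die within 14 days | OS given alive at 14 days | OS given alive at 28 days | Chance of any death among 10 within 14 days |
|---|---|---|---|---|
| 60% | 1.9% | 61.2% | 62.4% | 18% |
| 70% | 1.4% | 71.0% | 71.9% | 13% |
| 80% | 0.9% | 80.7% | 81.4% | 8% |

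The last column is 1 − (1 − p)^10, with p the unrounded 14-day probability. The average gain is 0.7 to 1.2 points for 14 days and 1.4 to 2.4 points for 28 days.

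**4. Effect when an exclusion happens.** The event counts are illustrative, since the documents give none. Intervals are 90% Clopper-Pearson, the exact binomial type named in Section 13: lower limit the 5% quantile of Beta(x, n − x + 1), upper limit the 95% quantile of Beta(x + 1, n − x). For x = n the lower limit is 0.05^(1/n); for 9/9 that is 0.717.

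| Scenario | All treated | At least two cycles |
|---|---|---|
| OS: one death, before Cycle 2 | 9/10 = 90% (60.6 to 99.5%) | 9/9 = 100% (71.7 to 100%) |
| OS: two deaths, one before Cycle 2 | 8/10 = 80% (49.3 to 96.3%) | 8/9 = 88.9% (57.1 to 99.4%) |
| OS: three deaths, two before Cycle 2 | 7/10 = 70% (39.3 to 91.3%) | 7/8 = 87.5% (52.9 to 99.4%) |
| Relapse: two, one before Cycle 2 | 2/10 = 20% (3.7 to 50.7%) | 1/9 = 11.1% (0.6 to 42.9%) |

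One removed early death moves OS by 10.0 points if it is the only death, and by 8.9 points if there are two.

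**5. Direction for other cases.** If the excluded subject never had chronic GvHD and four others did, crude incidence goes from 4/10 = 40% to 4/9 = 44%, which is unfavourable. If the one-dose subject survives and one other subject dies, OS goes from 9/10 = 90% to 8/9 = 88.9%. With no deaths, 10/10 and 9/9 are both 100%.

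**6. How often any subject would be lost.** If the chance of missing Cycle 2 for any reason is assumed at 2%, 5% or 10%, the chance of losing at least one of 10 is 1 − 0.98^10 = 18%, 1 − 0.95^10 = 40% or 1 − 0.90^10 = 65%.

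**The case against.** The strongest reply concerns size and visibility. The window is short, and entrants are in complete remission, MRD-negative and fully engrafted, with no uncontrolled illness. On the assumptions above, most such trials would see no death before Cycle 2, and the paired intervals overlap heavily. OS is defined with censoring, so a simple proportion is an illustration of the planned estimate; the two coincide only when everyone is followed to the time point. Early failures are not hidden either. Every treated subject is in the safety analysis to 30 days after the last dose, deaths are recorded on the Toxicity and Death Forms (Section 12.1), and a possibly related death suspends the study (Section 5.10). The trial is descriptive, so no type I error or power is affected. All of this stands, and it limits the weight of the point.

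A reader might also infer more than the documents support:
- That the rule always favours belimumab. It does so when the excluded subject had the event being counted. Step 5 shows the opposite for chronic GvHD, the trial's target, and for OS when the excluded subject survives.
- That one exclusion moves every secondary estimate. It need not, as 10/10 against 9/9 shows.
- That any severe acute GvHD before Cycle 2 removes the subject. Section 5.8 provides for a hold first, and a subject who improves within it can receive Cycle 2 and stay evaluable.
- That all secondary endpoints contain immortal time. Only OS and relapse are timed from the first dose in Section 8.2, and chronic GvHD on treatment does not of itself end treatment (Section 5).

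The reply does not remove the core. Section 8.2, as written, directs that a death or a treatment-ending relapse before Cycle 2 be left out of OS or relapse, and no other section puts it back. That a reader could restore the subject by hand is no reason to plan an estimate that needs restoring.

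**Conclusion.** The point holds as a defect in the definition of the analysis set. It builds about 14 days (11 to 17, or about 28 with a hold) of immortal time into OS and relapse, and excludes subjects for reasons related to outcome from all secondary endpoints. For OS and relapse, removing a subject who had the event improves the estimate; for chronic GvHD the effect can go either way.

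The expected bias is about 1 to 2 points on 12-month OS, assuming 60 to 80% survival and constant hazard. If early hazard after the first dose were higher than later, it would be larger; the documents give no basis for saying so. The practical issue is the single realised trial: one removed early death shifts OS by about 9 to 10 points when there are one or two deaths in all. That matters because the estimate is read against controls who face no stated equivalent condition, and feeds phase II planning. The change is worth making, but the rule does not undermine the primary safety objective, which already uses all treated subjects.

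**What to change.** In Section 8.2, replace the opening sentence so that every subject who receives any belimumab is analysed for all clinical secondary endpoints, with OS and relapse timed from C1D1. Keep the two-cycle set for the correlative summaries in Section 8.3, where a minimum exposure is defensible, and as a sensitivity analysis labelled as such.

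Reconcile Section 5.8, under which a subject with unresolved grade III-IV acute GvHD leaves the study, with Section 5.4, under which early discontinuers are followed on the study calendar. Without that, outcomes for some of these subjects may not be collected, and the wider analysis set would have gaps.

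The cost is a small text change in 8.2 and one clarification between 5.4 and 5.8. Follow-up of early discontinuers is already planned in Section 5.4. The OS and relapse estimates may become slightly less favourable; if nobody misses Cycle 2, no result changes. The fix does not give the controls a common starting point: trial subjects must first reach Day 30 to 80 in remission, and that guaranteed period needs its own matching rule.

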2.2 Secondary Objectives

1. To evaluate the impact of prophylactic belimumab on the incidence and severity of chronic GvHD at 6, 12 and 24 months after alloHCT
2. To evaluate the impact of prophylactic belimumab on the incidence and severity of acute GvHD at 3 and 6 months after alloHCT
3. To evaluate the impact of prophylactic belimumab on overall survival at 6, 12 and 24 months after alloHCT
4. To evaluate the impact of prophylactic belimumab on relapse rate at 6, 12 and 24 months after alloHCT
5. To evaluate the impact of prophylactic belimumab on overall corticosteroid requirement (dose and duration) for treatment of chronic GvHD at 6, 12 and 24 months after alloHCT
6. To evaluate the impact of prophylactic belimumab on the necessity to use alternative treatment modalities for chronic GvHD at 6, 12 and 24 months after alloHCT

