8.3 Exploratory Endpoints/Correlative Studies

Subjects who receive at least 2 cycles of belimumab are evaluable for explorative endpoints/correlative studies.

Age- and disease-matched controls with matched conditioning regimens and donor source/mismatch status will be obtained from the Bone Marrow Transplant Tissue Bank at Siteman Cancer Center at Washington University in St. Louis. These patients have had peripheral blood samples stored at time of transplant, 30 days post-transplant, 100 days post-transplant, 180 days post-transplant, and 360 days post-transplant. Immune competence and B cell phenotype subset panels will be performed on these samples. Additionally, BAFF levels will be measured and correlated with development of GvHD similarly to study cohort. The clinical outcomes including survival, recurrence rate, engraftment, incidence of acute and chronic GvHD, and medications list are readily available in institutional computerized database.

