12 DATA SUBMISSION SCHEDULE

Case report forms with appropriate source documentation will be completed according to the schedule listed in this section.

Case Report Form	Submission Schedule
On-Study Form	Prior to start of study treatment
Treatment Form Medical History Form	At the end of each cycle

Correlatives Form	Baseline Cycle 3 pre-treatment 6 mos post-C1D1 9 mos post-C1D1 1 yr post-C1D1 15 mos post-C1D1 18 mos post-C1D1 21 mos post-C1D1 Evidence of B-cell reconstitution 2 yrs post-C1D1 3 yrs post-C1D1 4 yrs post-C1D1 5 yrs post-C1D1
Treatment Summary Form	End of treatment
Acute GvHD Form	Baseline Cycle 3 Cycle 4 Cycle 5 Cycle 6 Cycle 7 6 mo f/u
Chronic GvHD Form	Cycle 3 Cycle 4 Cycle 5 Cycle 6 Cycle 7 6 mo f/u 9 mo f/u 12 mo f/u 15 mo f/u 18 mo f/u 21 mo f/u 24 mo f/u
Follow-Up Form	6 mos 9 mos 12 mos 15 mos 18 mos 21 mos 24 mos
Adverse Event Form Immunosuppressive Meds Form	Continuous
Progression Form	Time of progression
Death Form	Time of death

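### Acute GvHD is counted from transplant with no onset rule, so disease that began before belimumab can enter an endpoint meant to show the drug's effect

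*Combined protocol and SAP*

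**What the plan says.** The objective in Section 2.2 is causal in tone: "To evaluate the impact of prophylactic belimumab on the incidence and severity of acute GvHD at 3 and 6 months after alloHCT". The matching endpoint in Section 8.2 is "Incidence and severity of acute GvHD at 3 and 6 months after alloHCT", and the only text beneath it names the modified Minnesota-CIBMTR grading in Appendix F. Neither Section 8.2 nor Section 13 gives an onset rule, an at-risk definition, or a way to handle acute GvHD already present at first dose.

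Section 5 has subjects "enrolled in the study and start treatment between Day +30 and Day +80 after alloHCT". Section 5.2 repeats that window and then states a narrower one: "Cycle 1 of belimumab will be administered between Day +30 and +60 after alloHCT". On entry status, Section 5 says "At the time of enrollment, acute GvHD should be grade II or less" and lets subjects stay on steroids given for acute GvHD. Exclusion 1 in Section 3.2 bars only active grade III-IV disease and admits subjects whose earlier acute GvHD has resolved.

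Two neighbouring endpoints are handled differently. Overall survival and relapse also carry time points after alloHCT in their titles, but the text below fixes the origin, for example "Overall survival will be determined from date of belimumab initiation".

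The Acute GvHD Form in Section 12 is due at "Baseline Cycle 3 Cycle 4 Cycle 5 Cycle 6 Cycle 7 6 mo f/u", so status before the drug is collected. Section 13 makes matched institutional controls the comparator for preliminary efficacy. For those controls, Section 8.3 says "incidence of acute and chronic GvHD, and medications list are readily available in institutional computerized database".

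**The concern.** An endpoint meant to reflect a drug should not be credited or charged with events that happened before the first dose. Here such events are expected by design: treatment starts one to nearly three months after transplant, and a history of acute GvHD, or active disease up to grade II, is no bar to entry. Chronic GvHD does not share the problem, because subjects with chronic GvHD at enrollment are excluded.

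At stake is whether the 3- and 6-month acute GvHD figures can be interpreted. As defined, they mix events before and after belimumab in proportions that depend on each subject's start day and entry status. Section 13 says the data from this study will feed sample-size estimates for a later phase II study. A figure that mixes the two periods is a poor input for that.

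**Working it through.** **The plan's own figures.** No operating figure is given for acute GvHD. The two safety figures in Section 13 reproduce for n = 10 and are not affected:
- At least one serious adverse event at a true rate of 20%: 1 − 0.8^10 = 0.893 (stated as 90%).
- Two or more at a true rate of 5%: 1 − 0.95^10 − 10 × 0.05 × 0.95^9 = 0.086 (stated as less than 10%).

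**How much of each window precedes the drug.** Inputs are first dose on Day 30 to 80 (Section 5), or 30 to 60 (second statement in Section 5.2). I take 3 months as 91 days and 6 months as 183 days. The share is start day ÷ window length.

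| Start day | Share of 3-month window | Days left | Share of 6-month window | Days left |
|---|---|---|---|---|
| 30 | 30/91 = 33% | 61 | 30/183 = 16% | 153 |
| 60 | 60/91 = 66% | 31 | 60/183 = 33% | 123 |
| 80 | 80/91 = 88% | 11 | 80/183 = 44% | 103 |

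These are shares of calendar time, not of events. They show that pre-drug time is a large part of what is counted under either statement of the dosing window.

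**Weight of one case.** With 10 evaluable subjects, each case that predates the drug and is counted adds 1/10 = 10 points. Under the 90% exact binomial interval named in Section 13, 1 of 10 gives 0.5% to 39% and 4 of 10 gives 15% to 70%. Three such cases would move a reported result from the first line to the second. If fewer than 10 subjects receive the two cycles that Section 8.2 requires for secondary endpoints, each case weighs more.

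**Illustration under assumed rates.** The documents give no acute GvHD rates, so these are assumptions. Let q be the proportion with acute GvHD before first dose and r the proportion of the rest who develop it afterwards (worsening is ignored).
- Counted from transplant: q + (1 − q)r.
- Share of counted cases that predate the drug: q / [q + (1 − q)r].

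For q from 20% to 50% and r from 10% to 30%:
- The from-transplant figure runs from 0.2 + 0.8 × 0.1 = 28% to 0.5 + 0.5 × 0.3 = 65%, while new onset among those without earlier disease is 10% to 30%.
- The pre-drug share of counted cases runs from 0.2/0.44 = 45% to 0.5/0.55 = 91%.

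**Controls.** Sections 8.3 and 13 match on age, disease, conditioning and donor. Trial subjects have also survived to a start day between Day 30 and Day 80, were in remission on the Day +30 marrow, and had no active grade III-IV acute GvHD at entry. Nothing in either section applies those conditions, or a starting day, to the controls.

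**The case against.** The best defence is proportion. This is one of six secondary endpoints in a 10-subject safety pilot with no hypothesis test, and no decision rests on it. Baseline acute GvHD has its own assessment and form, and Section 5.1.2 documents earlier GvHD treatments, so a listing of 10 patients could separate old from new cases. All of that stands, and it limits the weight of the point. It does not supply the rule, because the plan never commits to the separation.

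The endpoint title could also mean status at 3 and 6 months rather than cumulative incidence. Even then, acute GvHD that began before the drug and persists would count.

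A from-transplant clock also fits Appendix A, which ends classic acute GvHD at 100 days. That is a good reason not to insist on moving the time points to first dose, and the fix below does not.

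A reader might infer three stronger things that the documents do not support:
- **That the window shares measure misclassified events.** They measure time. The number of subjects with acute GvHD before first dose is not stated.
- **That late starters have no scheduled acute GvHD assessment on drug before month 3.** Sections 10.1 and 12 go from baseline to Cycle 3, but the synopsis schema may show a GvHD assessment at Cycle 2. Its columns are too poorly aligned in the text available to settle this. Examinations are also scheduled at Cycles 1 and 2, and Section 5.8 requires evaluation for new rash, diarrhea or raised liver enzymes.
- **That comparison with controls would flatter belimumab.** No acute GvHD comparison is specified as such. Exclusion 1 bars only active severe disease, so resolved severe cases among trial subjects could still count. Controls described as having samples stored to day 360 may be selected for survival. The net direction cannot be established.

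**Conclusion.** The point holds as a defect of definition. Read literally, Section 8.2 puts acute GvHD that predates belimumab into an endpoint that Section 2.2 ties to belimumab's effect, while overall survival and relapse in the same section run from the first dose. The number of affected cases is unknown. Each is worth 10 points if 10 subjects are evaluable. The assumed-rate illustration shows that the distortion could be large, but it does not estimate it.

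For controls the conclusion is narrower. If acute GvHD is compared, the two groups are not selected alike and no landmark is stated. Which way that would bias the result is open.

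The sponsor should correct this. It does not threaten the primary safety objective, and the data collected on trial subjects already allow the correction.

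**What to change.** In Section 8.2, second endpoint:
- Count as incident only acute GvHD with onset, or worsening in grade, after the first dose of belimumab.
- Report acute GvHD present at or before the first dose separately, with its grade, using the baseline acute GvHD form and the recorded history.
- Keep the 3- and 6-month time points after transplant if wanted, and show a from-transplant tally as a supplement.

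In Section 13, for any comparison of acute GvHD with the matched controls: start each control on the post-transplant day that matches the subject's first dose. Include only controls who are alive, in remission and without active grade III-IV acute GvHD on that day, as far as the institutional database allows.

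For trial subjects the cost is wording, with no new assessments. For controls there is somewhat more analysis work, and some may be lost at the landmark. Section 8.3 says that incidence is available, but not that dated grades are, so the sponsor should check that before committing.

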10.2 Follow-Up Calendar

Follow-up visits start 4 weeks after the end of protocol treatment (6-month follow-up is 6 months post-C1D1 and 4 weeks post-C7D1).

	+6mo	+9mo	+12mo	+15mo	+18mo	+21mo	+24 mo	+3 yr	+4 yr	+5 yr
CBC	X									
CMP, LDH, phosphate, uric acid, magnesium	X									
Pregnancy test ¹	X									
Research blood ²	X	X	X	X	X	X	X	X ²	X ²	X ²
Acute GVHD assessment	X									
Chronic GVHD assessment	X	X	X	X	X	X	X			
Immunosuppressive medication assessment	X	X	X	X	X	X	X			
AE assessment	X									

1. Women of childbearing potential only

2. Once there is evidence of B cell reconstitution, additional blood will be drawn (refer to Section 9), and will continue on an optional basis at 3, 4, and 5 years post-C1D1

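### Survival and relapse are named in months after transplant but measured from belimumab start 30 to 80 days later, and 3-month acute GvHD includes time before the first dose

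*Combined protocol and SAP*

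**What the plan says.** Section 2.2 sets the survival objective as "overall survival at 6, 12 and 24 months after alloHCT", and words relapse the same way. Section 8.2 repeats this in the endpoint titles, "Overall survival at 6, 12 and 24 months after alloHCT" and "Relapse rate at 6, 12 and 24 months after alloHCT". The definitions under those titles use another origin: "Overall survival will be determined from date of belimumab initiation, with death from any cause as the event of interest", and "Relapse rate will be determined from date of belimumab initiation and censoring at last follow up date".

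The other four secondary endpoints (chronic GvHD, acute GvHD, corticosteroid requirement, alternative treatments) are also stated in months after transplant and are given no second origin. The acute GvHD endpoint reads "Incidence and severity of acute GvHD at 3 and 6 months after alloHCT".

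The synopsis, Section 5 and the first paragraph of Section 5.2 put the first dose between Day 30 and Day 80 after transplant. The second paragraph of Section 5.2 says Day 30 to Day 60. Visits run from the first dose; Section 10.2 says "6-month follow-up is 6 months post-C1D1 and 4 weeks post-C7D1". Under Section 12 the acute GvHD form is due at "Baseline Cycle 3 Cycle 4 Cycle 5 Cycle 6 Cycle 7 6 mo f/u", which matches the calendar in Section 10.1.

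Subjects are evaluable for secondary endpoints only after at least two cycles (Section 8.2). Section 13 plans an exact 90% binomial interval for preliminary efficacy, a comparison with tissue-bank controls, and use of the results to size a phase II study. It does not reconcile the two clocks and names no landmark or delayed-entry method.

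**The concern.** A proportion alive or relapsed needs one defined time point. For survival and relapse, an analyst who follows the title and one who follows the definition will report different numbers under the same label.

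The choice also matters for the comparison with controls. Eligibility requires remission and no chronic GvHD at enrolment, and evaluability requires a second cycle. If time is counted from transplant with no adjustment, treated subjects are credited with a stretch in which, by selection, they could not have died or relapsed. No matching condition is stated for controls.

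The acute GvHD endpoint has a different weakness. Its objective is the impact of belimumab, but part of the 3-month interval passes before any belimumab is given. Section 3 admits subjects with prior resolved acute GvHD, and Section 5 allows acute GvHD up to grade II at entry. The plan does not say whether acute GvHD before the first dose counts.

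**Working it through.** The plan gives no figure for this point. Its one design calculation, the chance of at least one serious adverse event in 10 subjects at a true rate of 20%, reproduces (1 − 0.8^10 = 0.893, against 90%) and plays no part here.

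**Inputs.** Start day s = 30 to 80 (synopsis, Sections 5 and 5.2), or 30 to 60 (second paragraph of Section 5.2). Infusions at weeks 0, 2, 4, 8, 12, 16 and 20 (Section 10.1). One month = 30.44 days.

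**1. Two readings of a horizon of m months (survival and relapse).** Counted from C1D1, it falls (30.44m + s)/30.44 months after transplant. Counted from transplant, it falls (30.44m − s)/30.44 months after C1D1.

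| m | From C1D1: months post-transplant, s = 30 / 60 / 80 | From transplant: months after C1D1, s = 30 / 60 / 80 |
|---|---|---|
| 6 | 7.0 / 8.0 / 8.6 | 5.0 / 4.0 / 3.4 |
| 12 | 13.0 / 14.0 / 14.6 | 11.0 / 10.0 / 9.4 |
| 24 | 25.0 / 26.0 / 26.6 | 23.0 / 22.0 / 21.4 |

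The gap is s/30.44 = 1.0 to 2.6 months (1.0 to 2.0 with the Day 60 limit).

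**2. Size on the survival scale.** The plan gives no survival rate. Assume a constant hazard and 60-80% alive 12 months after belimumab start (S12). The readings then differ by S12^((30.44m − s)/365.25) − S12^(30.44m/365.25).
- Largest at 6 months (S12 = 0.60, s = 80): 0.8663 − 0.7746 = 9.2 points.
- Smallest at 6 months (S12 = 0.80, s = 30): 0.9110 − 0.8944 = 1.7 points.
- At 12 months the range is 1.5 to 7.1 points; at 24 months, 1.2 to 4.3.

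In 10 subjects, 9.2 points is 0.92 of a patient.

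**3. Share of the acute GvHD interval before the first dose.** Three months is 91.3 days.
- s = 30: 30/91.3 = 33%
- s = 60: 60/91.3 = 66%
- s = 80: 80/91.3 = 88%

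The share passes one half at s = 91.3/2, about Day 46. For the 6-month endpoint (182.6 days) it is 16% at s = 30 and 44% at s = 80.

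**4. First scheduled post-baseline acute GvHD assessment.** This is C3, nominally Day s + 28. It falls after Day 91 when s is 64 or more, so for starts on Day 64-80. With the Day 60 limit the latest nominal C3 is Day 88, so this does not arise. The ±3-day windows on C2 and C3 allow C3 as early as 2 × 11 = 22 days after C1; on that best case the affected starts are Day 70-80.

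**5. Evaluability.** C2 is nominally Day s + 14. For s of 78 or more it falls after Day 91, so the 3-month point passes before the subject becomes evaluable.

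**6. Can the existing visits serve the transplant clock?** Six months post-transplant is 103 to 153 days after C1D1. C6 is at day 112 and C7 at day 140, so an assessment lies within about two weeks. Twelve and 24 months fall between 3-monthly visits, at most about 45 days from the nearest.

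**The case against.** The strongest reply is that this is a 10-subject descriptive pilot with a safety primary endpoint that is untouched, and that the survival gap is below one patient. That stands, and it keeps the point from being critical. It does not remove the contradiction, because the results are meant to feed a phase II sample size.

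A second reply is that the text can be reconciled: follow-up begins at belimumab, and results are reported at post-transplant times by a delayed-entry method. That would be coherent, but no section says so.

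A reader might infer more than the documents support:
- *That every secondary endpoint has two clocks.* Only survival and relapse do. The other four have one stated clock, and dated events can be placed on it whatever the visit calendar.
- *That 3-month acute GvHD is mostly pre-treatment.* This is true only for starts after about Day 45. For a Day 30 start it is one third.
- *That late starters have no acute GvHD data by Day 91.* The gap in scheduled assessments exists only under the Day 80 limit. Section 5.8 also requires evaluation of any new rash, diarrhoea or raised liver enzymes, and the calendar has an examination and chemistry at C2.
- *That control outcomes are counted from transplant.* Section 8.3 puts the control blood samples on the transplant clock. It states no origin for their clinical outcomes.

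**Conclusion.** The point holds and should be fixed, but it is not critical. As written, each survival and relapse horizon has two meanings 1.0 to 2.6 months apart (1.0 to 2.0 if the Day 60 limit applies). Acute GvHD at 3 months after transplant mixes untreated and treated time, with 33% to 88% of the interval before the first dose (33% to 66% with the Day 60 limit), so it cannot be read as an effect of belimumab.

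The start-day range comes from the documents, which disagree on its upper end. The survival difference of 1.2 to 9.2 points across the three horizons rests on an assumed constant hazard and an assumed 60-80% alive 12 months after belimumab start. The safety analysis is unaffected.

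**What to change.** - **Survival and relapse.** In the synopsis and Sections 2.2 and 8.2, state both at 6, 12 and 24 months after C1D1. This matches the stated origin and the visit schedule.
- **If post-transplant horizons are kept.** Use a delayed-entry (left-truncated) estimate that also handles the two-cycle rule, for example with entry at the second infusion. Until then an evaluable subject cannot, by definition, have died.
- **Controls.** In any comparison, count only controls who were alive, in remission and free of chronic GvHD at the matched subject's start day post-transplant, and count time from that day.
- **Acute GvHD.** Report acute GvHD that is new or worse after C1D1, at existing visits (C5 at +12 weeks, and +6 months). Report acute GvHD before C1D1 separately, as baseline.
- **Start window.** Reconcile the Day 60 and Day 80 limits in Section 5.2.

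The cost is wording, plus a landmark rule for selecting controls; no new visits are needed. The downside is that survival and relapse are no longer given in the usual months-after-transplant form, which the delayed-entry estimate can supply as a supportive result.
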